4.6.1 Dose Interruption and Stopping Rules

Adverse Events (AEs) of supine SBP decrease, supine DBP decrease, postural BP decrease, HR increase and HR decrease will be closely monitored. If such an AE occurs in patients taking the study drug, the Investigator must assess whether the AE meets the study drug interruption/stopping rules and proceed as recommended in the below table.

If the study drug is interrupted due to the criteria described in the table, the patient will be evaluated as part of an unscheduled visit to assess their status and the Investigator will determine next course of action. If necessary, subsequent visits to assess the outcome of the event will be scheduled. Once the re-start criteria are met, study drug will be re-started under medical supervision. Additional visits may be scheduled at the investigator's discretion to more closely monitor patient status.

Any patient that develops postural hypotension will not be discharged from the study site with study drug until the event completely resolves and safety and tolerability of the reduced dose in the patient is confirmed.

Amendment 02 (10 August 2017)

4.7 Method of Assigning Subjects to Treatment Groups

A computer-generated block randomization schedule generated by the Sponsor. or a nominated designee will randomly assign the second state of the area of the area of the second state of the area of the second state of the secon

4.8 Randomization and Blinding

4.8.1 Randomization

Subjects will be randomized after the Investigator has verified that they are eligible per criteria in Section 3.5 and Section 3.6. Subjects will then be enrolled into this study and assigned to APD371 25 mg TID or 100 mg TID according to a randomization schedule. Subjects will be randomized based on gender.

Randomization will take place across all study sites using a centralized master list held by the study manager. When a site is ready to enroll a subject, they will contact the study manager to get the appropriate dose group assignment and unique subject number. The subject's identification number will be used on all of that subject's case report forms (CRF). Any subject identification numbers that are assigned will not be reused even if the subject does not receive treatment. All subjects must start treatment within 1 week of randomization.

4.8.2 Blinding

For each dose cohort, the Sponsor, CRO, Study safety medical monitors, subjects, and personnel involved with the conduct of the study will be unblinded to the identity of study medication.

4.8.3 Maintenance of Randomization Codes

All personnel directly related to this study (i.e., Investigators, site personnel, monitors, CRO personnel, Sponsor personnel) will remain unblinded.

4.9 Concomitant Medications

All concomitant medications (over-the-counter [OTC] and prescribed) that are taken by subjects and all procedures that are performed during the Screening period and during the study will be documented in the electronic case report form (eCRF) with start date/time and stop date/time, if known.

Stable doses of non-narcotic prescription medications required for treatment of current medical conditions other than pain (e.g., hypertension, thyroid disease, diabetes) may be continued during the screening and study period. Doses may be adjusted as appropriate per usual standards of care.

4.9.1 Not permitted

- Hormonal contraceptives for pain relief within 30 days prior to the Screening Visit, during the Screening period, and for the duration of the study.
- Moderate or strong CYP3A4/5 inducers or inhibitors

4.9.2 Permitted

- Pain rescue medications during screening or the treatment period including:
 - For an inflammatory flare: prednisone at a dose of 40 mg orally daily, to be tapered by 5 mg per week.
 - For severe pain: hyoscyamine at a dose of 0.25 mg tid prn pain
- Pain relief medications such as NSAIDs, narcotic analgesics, or acetaminophen/paracetamol given at stable doses for at least 2 weeks prior to screening and for the duration of the study
- Stable dose of oral or topical 5-ASA for at least two* weeks prior to randomization; stable dose to be maintained on the 5-ASA compound at a constant dose at least through end of study
- Mesalamine or sulfasalazine for at least 4 weeks prior to randomization
- Azathioprine or 6-MP, or methotrexate for at least 8 weeks prior to screening
- Oral corticosteroid therapy (prednisone at a stable dose of 30 mg/day, budesonide at a dose ≤ 9 mg/day, or equivalent steroid) provided that the dose has been stable for the 2 weeks immediately prior to screening or for the two weeks immediately prior to randomization if corticosteroids are being tapered
- Dose regimens within the ranges approved by the FDA and stable for at least 8 weeks prior to screening for the following monoclonal anti-inflammatory drugs:
 - Infliximab
 - Adalimumab
 - Certolizumab pegol
 - Ustekinumab
 - Vedolizumab
- Probiotics (e.g., *Culturelle, Saccharomyces boulardii*) provided that the dose has been stable for the 2 weeks immediately prior to randomization
- Antidiarrheals (eg, loperamide, diphenoxylate with atropine) for control of chronic diarrhea
- Antibiotics used for the treatment of CD (i.e., ciprofloxacin, metronidazole) provided that the dose has been stable for the two weeks immediately prior to randomization and will remain stable throughout study participation

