8.10. Use of Rescue Medication

The number of subjects using rescue medication during the Screening period and at any time during active treatment will be tabulated by treatment group and overall by shift table. Because of the paucity of data with respect to changes, no inferential analyses will be conducted.

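### A rescue prednisone taper begun in screening cannot meet the steroid-stability rule in Protocol 4.9.2, and neither document says whether such a subject may be randomised or how the resulting Baseline is analysed

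*Protocol*

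**What the plan says.** Three entries in Protocol 4.9.2 bear on steroids and 5-ASA.

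- **Rescue.** The list opens with "Pain rescue medications during screening or the treatment period including" and, for an inflammatory flare, gives "prednisone at a dose of 40 mg orally daily, to be tapered by 5 mg per week".
- **Oral corticosteroids.** These are permitted "provided that the dose has been stable for the 2 weeks immediately prior to screening or for the two weeks immediately prior to randomization", the second limb applying to subjects on a taper. The prednisone figure here is a stable 30 mg/day. The synopsis gives at most 20 mg/day, on stable maintenance doses.
- **5-ASA.** One bullet reads "Stable dose of oral or topical 5-ASA for at least two* weeks prior to randomization" and continues "stable dose to be maintained on the 5-ASA compound at a constant dose at least through end of study". The next reads "Mesalamine or sulfasalazine for at least 4 weeks prior to randomization" and does not mention dose stability.

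Screening lasts up to 28 days (Protocol 3.1). Baseline AAPS is the mean over the 7 consecutive days ending with the last pre-treatment diary entry (SAP 3.3.2.1). CRP is drawn pre-dose on Day 1 (Protocol 5.9.4). The pre-treatment calprotectin sample is taken at some point in screening (Protocol 5.10). The synopsis names the subject's own screening baseline as the control.

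SAP 8.2 tests pooled AAPS change from Baseline at Wk 4 and Wk 8 with one-sample t-tests. SAP 8.6 and 8.7 test CRP and calprotectin change within treatment and overall. On rescue, SAP 8.10 says only "The number of subjects using rescue medication during the Screening period and at any time during active treatment will be tabulated", by shift table.

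**The concern.** The rescue bullet and the steroid-stability bullet meet in one subject: someone who flares in screening and starts the prednisone course. The first bullet permits the treatment; the second describes a condition the treatment cannot satisfy. The visible text does not say whether that subject is a screen failure, is re-screened, or is exempt, so sites may decide differently.

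If the subject is randomised, pain, CRP and calprotectin at Baseline are measured during or just before a steroid course that keeps changing through the first weeks of APD371. The within-subject change then mixes a drug effect with a steroid effect and recovery from a flare. The SAP gives no rule for such scores in 8.2, and its list of significant violations in 5.3 does not name unstable background therapy or rescue.

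**Working it through.** The plan has no figure to reproduce: Protocol 8.2 states that no sample-size or power calculation was made. The check is calendar arithmetic.

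**Inputs.** Course: 40 mg, less 5 mg each week (Protocol 4.9.2). Possible start days: Day -28 to Day -1. Stability: 14 days. Baseline week: taken as Day -7 to Day -1. Wk 4 target: Day 29 (SAP 4.7.2). Randomization to first dose: 0 to 7 days (Protocol 4.8.1). I assume no background prednisone before the course.

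**Formula.** Count days so that Day 1 is t = 0 and Day -1 is t = -1. For a course started on day s, dose(t) = max(0, 40 - 5 × floor((t - s)/7)) for t at or after s. Time to zero is 40/5 = 8 weeks, against at most 4 weeks of screening.

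| Start | Dose in Baseline week (mg) | Day 1 | Day 29 | First day at zero |
|---|---|---|---|---|
| Day -28 | 25 | 20 | 0 | Day 29 |
| Day -21 | 30 | 25 | 5 | Day 36 |
| Day -14 | 35 | 30 | 10 | Day 43 |
| Day -10 | 40 then 35 | 35 | 15 | Day 47 |
| Day -7 | 40 | 35 | 15 | Day 50 |
| Day -3 | 0 then 40 | 40 | 20 | Day 54 |
| Day -1 | 0 then 40 | 40 | 20 | Day 56 |

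**Stability rule.** Each step lasts 7 days, so no start gives 14 unchanged days before randomization: 0 of 28 starts with no gap, 0 of 21 with a 7-day gap. The first limb cannot be met by a course that did not yet exist before screening.

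**Baseline week.** The dose is constant through it only for starts on Day -28, -21, -14 and -7. In the other 28 - 4 = 24 it changes within the week, and even in those four the week is one step of a taper.

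**Direction.** A Day -28 start puts Baseline in the fourth week of prednisone. Relief from the course may already be in the Baseline, and withdrawal follows, so the change can be understated. A start in the last days before Day 1 puts most of Baseline in the flare, with the steroid response to come, so the change can be overstated. Because calprotectin is sampled in screening and CRP on Day 1, a course can also begin between the two.

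**Size (assumed; no effect figure is in the documents).** For an AAPS shift of 1 to 3 points in one subject: cohort of 8, 1/8 to 3/8 = 0.13 to 0.38; pooled 16, 1/16 to 3/16 = 0.06 to 0.19.

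**5-ASA.** Counting both periods as stability periods back from randomization, the last permitted change is Day -14 (no gap) or Day -21 (7-day gap) under two weeks, and Day -28 or Day -35 under four. All precede Day -7.

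**The case against.** The strongest reply is a dilemma. If the stability bullet governs, the subject is not randomised and no Baseline is affected; if rescue is exempt, the bullets do not conflict. That is fair, and it makes the point conditional. It does not settle it, because the visible text does not choose, and Protocol 3.4 lets the sponsor approve eligibility exceptions in advance. Much of the inclusion and exclusion list is not shown, and a governing rule may be there.

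It can also be said that medications are recorded with dates (Protocol 4.9), that rescue and concomitant medications are listed (SAP 13), and that AAPS and responder analyses are repeated Per Protocol. This stands in part. Listings identify a subject but do not show the result without that subject. The Per Protocol repeat removes one only if the case is called a major violation, and it is not planned for CRP or calprotectin. The analyses are exploratory with nominal p-values, and the primary objective is safety, which limits the stakes.

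Four stronger readings are tempting and not supported:

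- *5-ASA dose can change during Baseline.* Both windows close before Day -7. The bullets can also be read together as four weeks on drug, the last two at a stable dose. That they cover the same drugs is itself an assumption; the documents do not say mesalamine is a 5-ASA.
- *Baseline is the only control.* It is the named control, and the only one for pooled change, but the doses are also randomised and compared (Protocol 8.1).
- *The SAP 8.10 shift table shows that flare-prednisone subjects are expected.* Rescue also includes hyoscyamine (SAP 3.3.2.9), which alone could fill the table; SAP 8.10 also describes the data on changes as sparse.
- *The effect is large.* A 4-point fall would move a cohort mean by 4/8 = 0.5, but no such figure is in the documents, and it does not fit a Day -28 start, where a fall from the flare would largely precede Baseline.

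**Conclusion.** The point holds for steroids. A rescue prednisone course begun in screening cannot meet the stability rule in the same section, and whether such a subject may enter is not stated in the visible text. If one enters, the steroid dose is changing in or around the Baseline week and is 20 to 40 mg on Day 1 against 0 to 20 mg on Day 29. Change from Baseline in AAPS, CRP and calprotectin can then be biased either way, with no specified analysis that removes the subject.

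The size is modest per subject, on the assumed shifts above, but in a trial of about 16 a second affected subject in the same cohort would double the shift to 0.25 to 0.75. The conclusion rests on rescue not being exempt or excluded by criteria that are not shown, and on at least one such subject being enrolled; the number may be small or zero. The differing prednisone limits are a separate contradiction that holds regardless. The 5-ASA bullets are an eligibility ambiguity only.

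**What to change.** **Protocol.** Reconcile the rescue bullet with the steroid-stability bullet. State whether a subject who takes rescue prednisone in screening may be randomised and, if so, which diary week is Baseline. Reconcile the prednisone limits in the synopsis and 4.9.2 at the same time, and state one rule for 5-ASA, mesalamine and sulfasalazine. This review takes no position on which dose or period is right.

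**SAP.** From the recorded start and stop dates, flag every subject with rescue prednisone or a steroid change from the start of screening to Day 1. Repeat the AAPS, CRP and calprotectin change-from-Baseline analyses without them. If no subject is flagged, one sentence saying so is enough. Because the SAP amendment postdates database lock, label this as a post-lock sensitivity analysis.

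**Cost.** A protocol clarification and one extra sensitivity row, from data already collected, on a slightly smaller sample. With so few subjects, it should be read as a check on the direction and size of the estimate rather than on its p-value.

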4.10 Restrictions

4.10.1 Fluid and Food Intake

There are no food restrictions around dosing with the exception of grapefruit and prune juice. Subjects will be provided standardized meals (breakfast, lunch, dinner, snacks) per the Investigating site's SOPs while housed in the clinic. 240 mL of water will be administered with study medication in the clinic at the time of dosing on Day 1 and Week 8 when the PK profile will be obtained. Water may be provided at all other times as needed.

4.10.2 Activity

Subjects will not engage in strenuous activity at any time during study participation.

5 STUDY PROCEDURES

5.1 Informed Consent

For any subject to be screened the Investigator will obtain a signed Informed Consent Form (ICF). The ICF must be reviewed and approved by the Investigator's designated IRB and by the Sponsor. The ICF should include all the elements as outlined in Section 4.8.10 of the ICH guideline for GCP (E6).

All subjects will be informed in writing of the nature of the protocol and investigational therapy and its possible hazards, and of their right to withdraw at any time, before they will be permitted to sign the ICF. The subject's medical record should contain written documentation indicating that informed consent was obtained.

5.2 Medical History

During the Screening Visit, a complete medical history and a social history, including smoking, caffeine, and alcohol use, will be collected by subject interviewer. Concomitant medications, recent blood donations, illnesses, and participation in other investigational drug studies will also be recorded. A review of the subjects screening medical history will be performed at the time of presentation on Day 1 (pre-treatment) to update findings including the requirement for a AAPS \geq 4 (from a subject diary) and to document any pre-treatment AEs.

5.3 Physical Examination

Body measurements (height and weight) will be taken at the timepoints indicated in the Schedule of Events (Table 1). A complete physical examination including weight will be performed at the initial Screening visit. Abbreviated physical examinations (includes body weight and evaluation of changes to previously observed abnormal findings) will be completed at the time of presentation to the clinic prior to initial dose administration, at the Follow-up Visit Wk 10 and at early termination noting changes in any body system since the previous examination.

5.4 Vital Signs

Supine blood pressure, pulse rate, temperature, and respiratory rate will be measured after the subject has been resting in the supine position for 5 minutes at the timepoints indicated in the Schedule of Events (Table 1). All once daily vital sign assessments are take place before morning dosing or equivalent times when not dosed at approximately 08:00. Vitals signs will be measured after any 12-lead ECG measurement but prior to any blood draw that is scheduled at the same timepoint. Pulse rate will be measured with a pulse oximeter.

Active-Standing Test

The Active-Standing Test¹⁵ that measures BP and heart rate before and after changing the position from supine to standing will also be performed. The test will be performed by the

bedside by measuring blood pressure (BP) and heart rate after the subject has been resting in the supine position for 5 minutes and then after 1 and 3 minutes of standing.

The test will be performed at the following timepoints:

- Day 1: pre-dose, 2, 4, 6, 8 and 10 hours after first dose
- Day 2: 2, 4 and 6 hours after the first dose
- Week 1, 2, 4, 6, and 8 visits 2 hours after the first dose

The active-standing test will be performed if subjects discontinue the study (Early Termination).

5.5 Abdominal Pain assessment

5.5.1 Abdominal Pain Score and Average Abdominal Pain Score

The abdominal pain score (APS) is a PRO using an NCR rating scale which is recorded in a subject diary. The 11 point NCR scale ranges from 0 [no abdominal pain] to 10 [worst possible abdominal pain] will be recorded by subjects in a diary as follows;

During Screening. Twice daily for at least 7 consecutive days within the initial Screening period (Day -28 to Day-1), at the following times;

- 1. Early morning, approximately 06:00 08:00
- 2. Late evening, approximately 20:00 22:00.

The Screening assessment of AAPS will be based on the average of the last (most recent) 7 days of morning and evening diary records within the screening period.

During Treatment. Three times a day on each treatment Day (Day 1 to 56) at the following times;

- 1. Before the morning dose and before any other morning dose study procedures
- 2. Approximately at 1.5 hours after the morning dose
- 3. Before the evening dose.

Note: Subjects will also be required to complete the diary before their first morning dose on Wk 0 (Day 1), and at the End-of-Treatment Visit at Wk 8 in the early morning (06:00 - 08:00). If a subject discontinues the study, Early Termination, the APS score will be assessed.

The average abdominal pain Score (AAPS) is the average of the APS score over each weekly assessment period (Wk 1 to Wk 8). These average scores will be determined automatically in the eCRF from the diary cards records inserted into the eCRF.

If a subject changes dose during the course of the study, they will maintain their daily APS scoring.

5.8 Electrocardiography

5.8.1 12-lead Safety Electrocardiograms

Safety 12-lead ECGs will be recorded from an ECG machine and will be printed and reviewed on site by the Investigator or designee. Typically, all 12-lead ECGs will be obtained as single tracings, with the exception of the pre-treatment ECG obtained on Day -1, which will be a triplicate recording. If a 12-lead ECG shows an abnormality, then two additional ECGs should be obtained as soon as possible for confirmation. Abnormalities of particular interest include increased PR or corrected QT (QTc) intervals, either absolute prolongations or clinically noteworthy increases from baseline values.

Electrocardiograms will be recorded with subjects resting in the supine position. Subjects will have been in the supine position for 10 minutes prior to ECG recording, which will be performed prior to any vital sign measurement and/or blood draw that may be scheduled at the same time point.

Intervals to be provided on the confirmed read for each 12-lead ECG are: RR, PR, QRS, QT, QTc, QTcB, and QTcF. All interval measurements will be made from a single lead (lead II). If lead II is unsuitable for measurement, the following lead progression will be used: I, V4, V5, V3, any suitable lead.

The Investigator will be responsible for review and interpretation of 12-lead ECGs on site and for determining if the ECG is normal, abnormal clinically insignificant, or abnormal clinically significant. Findings will be documented in the eCRF. This information will be used in the ongoing safety review during the conduct of the study.

A 12-lead ECGs will be collected at Screening; at the start of Wk 0 (Day 1) and at Wk 8 (Day -1) prior to and 1.5 hours after the first daily dose; and at the Follow-up Visit at Wk 10. 12-lead ECGs will be collected prior to any vital sign measurement and/or blood draw that is scheduled at the same time point.

5.9 Clinical Laboratory Tests

Protocol-required laboratory testing will be collected during initial screening to determine eligibility. Clinical laboratory tests will be repeated at pre-treatment on Wk 0 (Day 1), pre-treatment at the end of Wk 4 and 8 (Day -1), at the Follow-up visit (Wk 10) and in the event of early termination.

All details regarding clinical laboratory sample collection, preparation, and shipment are included in the laboratory manual provided by the local or central laboratory and the PK sample collection manual provided by the Sponsor.

In the event of abnormal clinical laboratory values, the Investigator will make a judgment whether or not the abnormality is clinically significant.

5.9.1 Laboratory Parameters

Clinical laboratory tests will include the following:

Serum Chemistry

Aspartate transaminase Alanine transaminase Alkaline phosphatase Gamma-glutamyl transferase Bicarbonate Magnesium Sodium Potassium Chloride Calcium Inorganic phosphate Glucose Amylase Bilirubin (total) Creatinine Blood urea nitrogen Total protein Albumin Creatine kinase and MB subtype (if elevated) Lactate dehydrogenase Lipase Total Cholesterol Triglycerides

Hematology

White blood cell count (WBC) Red blood cell count Hemoglobin Hematocrit Mean cell volume Mean cell hemoglobin Platelet count Differential WBC

Urinalysis

Appearance Color Specific gravity pH Protein Glucose Ketones Leukocyte esterase Blood Bilirubin Urobilinogen

Coagulation

Prothrombin time Activated partial thromboplastin time

Other

Serum/urine pregnancy test (females only), Thyroid function tests [(TSH, T4, and free T4) - Screening only], Hs CRP

5.9.2 Virology

Human immunodeficiency virus (HIV) antibody, hepatitis B surface antigen (HBsAg), and hepatitis C virus (HCV) Screening tests will be performed at the Screening Visit only.

